#### **14.9 Quality Assurance**

Quality assurance audits of select patients and source documents may be conducted by the Quality Assurance and/or Data Safety Committees at participating institutions or UC Davis Cancer Center as outlined in the UC Davis Cancer Center Data and Safety Monitoring plan.

## 15. OVERSIGHT AND MONITORING

### 15.1 Data and Safety Monitoring

In addition to the requirements for adverse event reporting as outlined in Section 7.0, this protocol is also subject to the UC Davis Cancer Center's (UCDCC) Data and Safety Monitoring Plan. The UCDCC is committed to pursuing high-quality patient-oriented clinical research and has established mechanisms to ensure both scientific rigor and patient safety in the conduct of clinical research studies. The UCDCC relies on a multi-tiered committee system that reviews and monitors all cancer clinical trials and ensures the safety of its participants, in compliance with institutional and federal requirements on adverse event (AE) reporting, verification of data accuracy, and adherence to protocol eligibility requirements, treatment guidelines, and related matters. The Scientific Review Committee (SRC) assumes overall oversight of cancer studies, with assistance and input from two independent, but interacting, committees: the Quality Assurance Committee and the Data and Safety Monitoring Committee. A multi-level review system strengthens the ability of the UCDCC to fulfill its mission in conducting high quality clinical cancer research.

The principal investigator (PI) and clinical research coordinator will meet at least monthly for ongoing study information, to discuss patient data and adverse events and to determine if dose escalation is warranted, when applicable.

According to the UCDCC Data and Safety Monitoring Plan, any new serious adverse events related to the drugs being used on this trial are reviewed monthly by the UCDCC Data and Safety Monitoring Committee and any applicable changes to the study are recommended to the PI, if necessary.

The UCDCC SRC determines if a UCDCC Data and Safety Monitoring Board (DSMB) is required. If required, the Data and Safety Monitoring Committee will appoint a DSMB. The DSMB is responsible for reviewing study accrual logs, adverse event information and dose escalation meeting minutes (where applicable) to ensure subject safety and compliance with protocol defined guidelines.

The Research Monitor is responsible to oversee the safety of the research and report observations/findings to the IRB or a designated institutional official. The Research Monitor will review all unanticipated problems involving risks to subjects or others associated with the protocol and provide an independent report of the event to the IRB. The Research Monitor may discuss the research protocol with the investigators; shall have authority to stop a research protocol in progress, remove individual human subjects from a research protocol, and take whatever steps are necessary to protect the safety and well-being of human subjects until the IRB can assess the monitor's report; and shall have the responsibility to promptly report their observations and findings to the IRB or other designated official and the HRPO.

## 15.2 Investigator Monitoring Guidelines

Investigators will conduct continuous review of patient safety. As mentioned in section 3.0, patients will be monitored weekly during the 30 day DLT period and every 30 days for the remaining of the study. All patients on active treatment will be discussed at weekly conferences that are held at the University of California Davis. Per Cancer Center guidelines, a trial cannot proceed to the next dose level until a DLT meeting is conducted to comprehensively review all toxicity data and approve the dose de-escalation. The discussion will include for each dose level: the number of patients, significant toxicities as described in the protocol, doses adjustments, and responses observed.

All patients will be monitored for a minimum of 12 months to evaluate for long-term radiation effects. Preliminary efficacy as determined by ARR, ORR, DCR and DFS will be assessed every 60 days during the study period.

**17. APPENDICES****17.1 Appendix 1: Performance Status Scale**

Karnofsky Status	Karnofsky Grade**	ECOG Grade	ECOG Status**
Normal, no complaints	100	0	Fully active, able to carry on all pre-disease performance without restriction
Able to carry on normal activities. Minor signs or symptoms of disease	90	1	Restricted in physically strenuous activity but ambulatory and able to carry out work of a light or sedentary nature, e.g., light house work, office work
Normal activity with effort	80		
Care for self. Unable to carry on normal activity or to do active work	70	2	Ambulatory and capable of all selfcare but unable to carry out any work activities. Up and about more than 50% of waking hours
Requires occasional assistance, but able to care for most of his needs	60		
Requires considerable assistance and frequent medical care	50	3	Capable of only limited selfcare, confined to bed or chair more than 50% of waking hours
Disabled. Requires special care and assistance	40		
Severely disabled. Hospitalization indicated though death nonimminent	30	4	Completely disabled. Cannot carry on any selfcare. Totally confined to bed or chair
Very sick. Hospitalization necessary. Active supportive treatment necessary	20		
Moribund	10		
Dead	0	5	Dead

\* KPS will be used in this study. ECOG status is listed for reference.

## 17.2 Appendix 2: Study Registration

- A. Registrations for this protocol must be made through the department of radiation oncology, University of California, Davis Cancer Center between normal business hours (Pacific Time), Monday through Friday (except holidays). Documentation of current IRB approval of this protocol by non-UCD institutions must be on file prior to registration of patients at these institutions.
- B. Pre-study laboratory tests, scans, and x-rays, must be completed prior to registration, within the time frame specified in the protocol. The eligibility checklist must be completed. Patients must sign an informed consent prior to registration.
- C. If the patient is to be registered the same day as the proposed treatment start date, the UC Davis Study Coordinator must be notified by fax ( [REDACTED] ) and/or email 24 hrs prior to proposed treatment start date that the site has a patient to register.
- D. Patients may be registered up to 72 hrs prior to treatment initiation. The signed consent, completed checklist and reports from all pre-study laboratory tests, scans and x-rays must be faxed/email to the University of California, Davis Comprehensive Cancer Center Office of Clinical Research in order to register the patient. The UC Davis Study Coordinator will review these documents and fax a registration confirmation within 24 hours. **NOTE: Administration of study medication may not be initiated until the registration confirmation has been received.**
- E. A patient failing to meet all protocol requirements may not be registered. If you have any questions regarding eligibility, please contact the PI or Study Coordinator

### 17.3 Appendix 3: Data Submission Schedule

All data will be collected using UC Davis data collection forms. Any and all source documentation should be maintained.

- SUBMIT WITHIN 24 HOURS OF REGISTRATION:  
Patient Registration Form
- SUBMIT WITHIN 14 DAYS OF REGISTRATION:  
In-House Pre-Study Evaluation Form (IH-102)
- SUBMIT WITHIN 7 DAYS OF SCREENING FAILURE:  
Patient Screen Failure Form
- SUBMIT WITH 14 DAYS OF CYCLE COMPLETION:  
Adverse Event/Drug Relationship Form
- SUBMIT WITHIN 14 DAYS OF END OF EACH TREATMENT CYCLE:  
In-House Treatment Cycle Form – Infusion
- SUBMIT WITHIN 14 DAYS OF EACH RESPONSE ASSESSMENT:  
Tumor Measurement Log
- SUBMIT WITHIN 14 DAYS OF OFF TREATMENT:  
Off Treatment/In Follow-up/Off Study/Expiration Form (IH-301)
- SUBMIT WITHIN 14 DAYS OF KNOWLEDGE OF DEATH IF PATIENT IS STILL ON STUDY OR 30-DAYS IF OFF STUDY:  
Off Treatment/In Follow-up/Off Study/Expiration Form (IH-301)
- SUBMIT WITHIN 2 DAYS OF KNOWLEDGE OF PROTOCOL DEVIATION:  
Clinical Trials Support Unit: Notice of Protocol Deviation
- SUBMIT WITHIN 14 DAYS OF EACH REQUIRED FOLLOW-UP ENCOUNTER:  
Follow-Up Form (IH-302)
- ALL SERIOUS ADVERSE EVENTS MUST BE REPORTED AS OUTLINED IN THE PROTOCOL.

## 17.4 Appendix 4: Molecular Correlative Sample Handling

### **Specimen Submission for Correlative Studies:**

Participation in these molecular correlative studies is mandatory. With the patient's consent, tissue and blood specimens will be submitted as outlined below. Samples will be de-identified and coded with a new patient ID number to protect patient's identity.

A specimen submission form should be filled out for each specimen obtained. All specimens must be labeled with protocol number, site identification, patient registration number, date of specimen collection, and number of cells (for PBMCs) or weight of tissue (for tissue biopsies). Correlative studies will be performed at UC Davis or samples will be shipped in a de-identified manner to other institutions / companies for analysis.

For correlative studies the following samples should be collected:

- 1) Peripheral blood samples obtained pre-treatment on day 1, then again at day 16 and at the q60 day follow-up visits.
- 2) Fresh tumor biopsy pre-treatment on day 1 and at day 15. Optional biopsy at progression.
- 3) Stool sample collected pre-treatment.

Correlative studies will include (in order of priority):

#### Blood

- 1) Flow Cytometry quantification, immunophenotyping, and activation / functional assessment of tumor infiltrating immune cells including myeloid-derived suppressor cells (MDSC), regulatory T (Treg) cells, T/B/NK cell immunophenotyping and activated T cells
- 2) RNA extraction for qPCR and Nanostring analysis
- 3) Whole exome sequencing (WES) as a normal tissue control to identify putative neo-antigens
- 4) Evaluation of systemic plasma tryptophan to kynurenine ratios
- 5) Peripheral blood cytokine / chemokine profiling by Luminex
- 6) T-cell receptor (TCR) deep sequencing to determine clonal expansion of T-cells in the systemic circulation
- 7) Other studies as deemed feasible and informative by the principal investigators

#### Tissue

- 1) IHC to assess tumor infiltrating immune cells (CD8, CD4, FoxP3) and expression of other markers with potential prognostic and/or predictive value on efficacy outcomes including IDO, PD-1 and PD-L1 as well as new biomarkers.
- 2) RNA extraction for qPCR and Nanostring analysis

- 3) Identification of tumor neo-antigens by RNA deep sequencing in conjunction with peripheral blood WES data.
- 4) Other studies as deemed feasible and informative by the principal investigators

#### Stool

- 1) Stool microbiomes analysis by 16s RNA sequencing

## 1.0 Peripheral Blood

### 1.1 Blood Collection

Blood specimens (4 x 5ml lavender top EDTA tubes) will be collected from each patient prior to initiating treatment at day 1 then again at Day 15 and at q60 day follow up visits as indicated in the study calendar. It is important that each tube be filled to 5ml to ensure sufficient specimens for the planned analyses. If possible, a blood specimen should be obtained at the time the patient is removed from protocol treatment or if the patient's disease progresses.

### 2.2 Blood Specimen Processing and handling – lavender top EDTA tubes

Four 5ml lavender top EDTA tubes will be collected from each patient at each time point. Each purple-top (EDTA) tube should be inverted several times, placed on wet ice, and delivered to the lab immediately. Every effort should be made to process blood samples within 1 hour of collection. Samples should be processed in sterile fashion.

The tube should be centrifuged as soon as possible at approximately 1,000-1,500 rpm (400 x g) for 10 minutes. The Plasma layer should be removed and kept on ice (see 1.2.1). PBMCs should be separated using sterile and endotoxin free Ficoll density gradient solution. The peripheral blood mononuclear cells (PBMCs) should be removed and pooled. The PBMC layer should be resuspended in three times the volume of cold sterile PBS. Cells should be counted using a hemocytometer and the total cell number should be noted. The expected yield is 1-2 million cells per ml of blood.

#### **The PBMCs collected from 4 lavender top tubes will be divided into three aliquots.**

Roughly half of the cells should be cryopreserved for future analysis. The second aliquot consisting of roughly 25% of the cells will be placed in RNAlater and snap frozen with liquid nitrogen and stored at -70 to -80°C for future RNA extraction. The third aliquot consisting of the last 25% of cells will be snap frozen in liquid nitrogen and stored at -70 to -80°C for future DNA extraction. If there are more than  $20 \times 10^6$  viable cells the RNA and DNA extraction aliquots should be limited to a total of  $5 \times 10^6$  cells each and the additional cells should be cryopreserved thus deviating from the 2:1:1 aliquoting.

### *1.2.1 Blood plasma*

The removed plasma layers should be pooled and centrifuged at 1000 x g for 10 minutes to clarify the plasma. The plasma should then be placed in up to eight 0.5 ml aliquots in labeled cryotubes. Any additional plasma can be discarded. The plasma will be frozen (snap frozen with liquid nitrogen if possible) and stored at -70 to -80°C. Samples should be batched and shipped overnight on dry ice to UC Davis at the address indicated. One to two tubes of plasma per patient will be shipped to Transgene in a batched manner from UC Davis.

### *1.2.2 Cryopreservation*

After counting, PBS washed PBMCs should be divided into aliquots of 5 million cells and spun down at approximately 1,000-1,500 rpm (400 x g) for 10 minutes. Each aliquot should be resuspended in 1ml of cold sterile CryoStor CS10 freeze media (catalog number 07930, STEMCELL technologies) which contains 10% DMSO. Each 1ml aliquot should be placed in a cryopreservation tube and the lid should be tightly secured. Tubes should be placed into a “[name]” or other slow freeze container and placed into a -70 to -80°C freezer for 12-24 hours. Tubes should then be transferred to and stored in vapor phase liquid nitrogen (-135°C). In a batched manner tubes should be shipped overnight in liquid nitrogen to UC Davis at the indicated address.

### *1.2.3 RNA later*

After counting, PBS washed PBMCs should be spun down at approximately 1,000-1,500 rpm (400 x g) for 10 minutes. The cell pellet should be re-suspended in 1ml of RNAlater solution snap frozen in liquid nitrogen and stored at -70 to -80°C. In a batched manner tubes should be shipped overnight on dry ice to UC Davis at the indicated address. Please note that PAXgene tubes will not be used for collection of PBMCs for RNA analysis.

### *1.2.4 Snap frozen for DNA extraction*

This specimen will be collected from the pre-treatment blood draw only. After counting, PBS washed PBMCs should be spun down at approximately 1,000-1,500 rpm (400 x g) for 10 minutes. The cell pellet should be snap frozen in liquid nitrogen and stored at -70 to -80°C. In a batched manner tubes should be shipped overnight on dry ice to UC Davis at the indicated address.

## 1.3 Peripheral Blood Analysis

### *1.3.1 Plasma*

Plasma samples will be stored at UC Davis for batched analysis. Plasma will be interrogated for chemokine and cytokine levels using the luminex platform. Additionally, plasma samples will be evaluated for tryptophan to kynurenine ratios.

### *1.3.2 Cryopreserved samples*

Cryopreserved samples will be stored at UC Davis for batched analysis. Samples will be thawed and stained with fluorophore-conjugated antibodies against CD4, CD8, CD25, CD62L, CD45RA, CD127, ICOS, PD-1, PD-L1, FoxP3, CD3, CD56, CD16, CD83, TIM-3, Ki-67, CD19, CD20, CD33, CD15, CD11b, HLA-DR and others. Stained cells will be interrogated by flow cytometry and results analyzed using FlowJo software.

### *1.3.3 RNAlater samples*

Cells in RNA later will be stored at UC Davis for batched analysis. Samples will be thawed and RNA will be extracted. The transcriptome will be analyzed using a nanostring 770 gene panel. Targeted RT-PCR will be used to validate genes of interest.

### *1.3.4 Snap frozen samples*

Snap frozen cell pellets will be stored at UC Davis for batched analysis. Samples will be thawed and genomic DNA will be extracted. Whole exome sequencing will be performed using the Illumina HiSeq platform.

## **2.0 Fresh tumor biopsy**

### 2.1 Tumor biopsy collection

Fresh tumor biopsy is collected pre-treatment and at day 15. Optional biopsy can be obtained at progression. Tumor biopsies should be collected by core needle biopsy using the largest bore needle and number of passes deemed safe. The same lesions should be targeted for all fresh tissue biopsies. Confirmation that the core biopsies contain tumor should be performed at the time of biopsy using touch prep.

### 2.2 Tumor biopsy processing and handling

On site at the time of the biopsy tumor tissues should be aliquoted into two portions. The top priority assay is IHC/IF and biopsy samples should be placed in formalin fixative and later embedded into FFPE blocks. In general samples should be placed in fixative at a 10:1 ratio and fixed for at least 48 hours but thicker tissue samples may require longer fixation.

If sufficient tissue is available (which there generally should be if more than one biopsy pass has been undertaken) then no less than 10mg and but preferably 20 - 50mg of tumor tissue should be placed in 1ml of RNAlater snap frozen in liquid nitrogen and stored at -70 to -80°C.

### 2.3 Tumor biopsy analysis

FFPE tissue biopsy blocks will be collected and stored at UC Davis. Tissues will be sectioned, prepared, and mounted for IHC/IF using standard procedures. When possible, IHC/IF should be performed within two weeks of slide sectioning. Biopsy samples will be stained by multiplex IHC/IF at UC Davis or collaborating laboratories to immunologically profile the tumor microenvironment. Markers examined will include CD3, CD8, CD4, FoxP3, Ki-67, PD-1 and PD-L1.

Tissue in RNA later will be stored at UC Davis for batched analysis. Samples will be thawed and RNA will be extracted. The transcriptome will be analyzed using a nanostring 770 gene panel. Targeted RT-PCR will be used to validate genes of interest. RNAseq data will also be used in conjunction with PBMC WES to identify mutational load and putative neoantigens.

## **3.0 Stool Sample Collection**

### 3.1 Stool sample collection

Stool samples will be collected by the patient pre-treatment using the provided stool collection kit. Stool samples will be stored on ice in the kit provided and returned to UC Davis preferably within 12 hours (an no longer than 24 hours) of collection.

### 3.2 Stool sample processing and handling

Stool samples will be snap frozen in liquid nitrogen and stored at -70 to -80°C for batched analysis.

### 3.3 Tumor biopsy analysis

16s RNA will be extracted and sequenced from stool samples to determine the microbiome profile.

## 17.5 Appendix 5: Anaphylaxis Precautions

### EQUIPMENT NEEDED

- Tourniquet
- Oxygen
- Epinephrine for subcutaneous, intravenous, and/or endotracheal use in accordance with standard practice
- Antihistamines
- Corticosteroids
- Intravenous infusion solutions, tubing, catheters, and tape

### PROCEDURES

1. In the event of a suspected anaphylactic reaction during drug administration, the following procedures should be performed:
2. Stop the study drug administration.
3. Apply a tourniquet proximal to the injection site to slow systemic absorption of drug. Do not obstruct arterial flow in the limb.
4. Maintain an adequate airway.
5. Administer antihistamines, epinephrine, or other medications as required by patient status and directed by the physician in charge.
6. Continue to observe the patient and document observations.

## 17.6 Appendix 6: Immune-Related Response Criteria

Increasing clinical experience indicates that traditional response criteria (e.g., Response Evaluation Criteria in Solid Tumors, Version 1.1 [RECIST v1.1] and World Health Organization [WHO]) may not be sufficient to characterize fully activity in the new era of target therapies and/or biologics. In studies with cytokines, cancer vaccines, and monoclonal antibodies, complete response, partial response, or stable disease has been shown to occur after an increase in tumor burden as characterized by progressive disease by traditional response criteria. Therefore, conventional response criteria may not adequately assess the activity of immunotherapeutic agents because progressive disease (by initial radiographic evaluation) does not necessarily reflect therapeutic failure. Long-term effect on the target disease must also be captured. The immune-related response criteria (irRC) are criteria that attempt to do that by enhancing characterization of new response patterns that have been observed with immunotherapeutic agents (i.e., ipilimumab) [57]. (Note: The irRC only index and measurable new lesions are taken into account.)

### GLOSSARY

Term	Definition
SPD	Sum of the products of the two largest perpendicular diameters
Tumor burden	$SPD_{\text{index lesions}} + SPD_{\text{new, measurable lesions}}$
Nadir	minimally recorded tumor burden
irCR	immune-related complete response
irPD	immune-related progressive disease
irPR	immune-related partial response
irSD	immune-related stable disease
irBOR	immune-related best overall response

### BASELINE ASSESSMENT USING irRC

**Step 1.** Identify the index lesions (five lesions per organ, up to ten visceral lesions and five cutaneous lesions).

**Step 2.** Calculate the SPD of all of these index lesions:

$$SPD = \sum_i (\text{Largest diameter of lesion } i) \times (\text{Second largest diameter of lesion } i).$$

POST-BASELINE ASSESSMENTS USING irRC

**Step 1.** Calculate the SPD of the index lesions.

**Step 2.** Identify new, measurable lesions ( $\geq 5 \times 5$  mm; up to five new lesions per organ: five new cutaneous lesions and ten visceral lesions).

**Step 3.** Calculate the SPD of the new, measurable lesions.

**Step 4.** Calculate the tumor burden:

$$\text{Tumor burden} = \text{SPD}_{\text{index lesions}} + \text{SPD}_{\text{new, measurable lesions}}$$

**Step 5.** Calculate the change in tumor burden relative to baseline and the change in tumor burden relative to nadir.

**Step 6.** Derive the overall response using the table below.

Overall Response	Criterion
irCR	Complete disappearance of all lesions (whether measurable or not, and no new lesions) confirmed by a repeat, consecutive assessment $\geq 4$ weeks from the date first documented
irPR	Decrease in tumor burden $\geq 50\%$ relative to baseline confirmed by a consecutive assessment $\geq 4$ weeks from the date first documented
irSD	Criteria for irCR, irPR, and irPD are not met; does not require confirmation
irPD	Increase in tumor burden $\geq 25\%$ relative to nadir confirmed by a consecutive assessment $\geq 4$ weeks from the date first documented

irCR = immune-related complete response; irPD = immune-related progressive disease; irPR = immune-related partial response; irSD = immune-related stable disease.

DETERMINATION OF irBOR

Once a patient has completed all tumor assessments, his/her irBOR may be determined:

Condition	irBOR
At least one irCR	irCR
At least one irPR and no irCR	irPR
At least one irSD and no irCR and no irPR	irSD
At least one irPD and no irCR, no irPR, and no irSD	irPD

irBOR = immune-related best overall response; irCR = immune-related complete response; irPD = immune-related progressive disease; irPR = immune-related partial response; irSD = immune-related stable disease.

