### 8.2 Discontinuation Due to Disease Progression

Immunotherapeutic agents such as epacadostat and SD-101 may produce antitumor effects by potentiating endogenous cancer-specific immune responses. The response patterns seen with such an approach may extend beyond the typical time course of responses seen with cytotoxic agents and can manifest as a clinical response after an initial increase in tumor burden or even the appearance of new lesions.

Immune related RECIST will be used for assessment of tumor response for the purposes of managing subjects on Protocol treatment and decision making for discontinuation of study therapy due to disease progression. PD should be confirmed no earlier than 4 weeks later according to the criteria outlined in Table 8. Subjects who are deemed clinically unstable or who have biopsy proven new metastatic lesions are not required to have repeat imaging for confirmation. This decision will be based on clinical judgment of a subject's overall clinical condition, including performance status, clinical symptoms, and laboratory data. At a minimum, subjects must meet the following criteria for continued treatment on study after disease progression is identified at a tumor assessment:

When feasible, subjects should not be discontinued until progression is confirmed; however, the decision to continue study treatment after the first evidence of disease progression is at the investigator's discretion based on the clinical status of the subject.

Subjects may receive study treatment while waiting for confirmation of PD if they are clinically stable as defined by the following criteria:

- No decline in ECOG performance status.
- Absence of new or worsening symptoms.
- Absence of rapid progression of disease.
- Absence of progressive tumor at critical anatomical sites (e.g., spinal cord compression) requiring urgent alternative medical intervention.

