**Table 8: Imaging and Treatment after First Radiologic Evidence of Progressive Disease**

	Clinically Stable		Clinically Unstable	
	Imaging	Treatment	Imaging	Treatment
First radiologic evidence of PD	Repeat imaging at $\geq 4$ weeks to confirm PD	May continue study treatment at the investigator's discretion while awaiting confirmatory scan	Repeat imaging at $\geq 4$ weeks to confirm PD if possible	Discontinue treatment
Repeat scan confirms PD	No additional imaging required	Discontinue treatment	No additional imaging required	N/A
Repeat scan shows SD, PR, or CR a	Continue regularly scheduled imaging assessments every 6 weeks from Week 12 to Week 48 then every 12 weeks thereafter.	Continue study treatment at the investigator's discretion	Continue regularly scheduled imaging assessments every 6 weeks from Week 12 to Week 48 then every 12 weeks thereafter.	May restart study treatment if condition has improved and/or clinically stable per investigator's discretion

a SD, PR, CR is based on new baseline from first evidence of PD.

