## Immune Related Response Criteria

A growing body of literature indicates that radiographic responses to immunotherapy may have different patterns and kinetics than what would be expected with traditional cytotoxic therapies. To account for these differences we will also characterize radiographic outcomes using the immune related response criteria outlined by Wolchok and colleagues [57]. See Appendix 6. This criteria will be used to measure the abscopal response rate and DCR (CR+PR+SD) and determine whether the study should proceed to stage 2 and is worthy of further study during the Simon two-stage study.

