## **Confirmation**

The main goal of confirmation of objective response is to avoid overestimating the response rate observed. For reporting the study outcomes the response rate and confirmed response rate will be made clear. For interval evaluation of response rates during the Simon-two stage study responses do not need to be confirmed for the study to progress. To be assigned the status of confirmed responses must be confirmed by repeat assessments that should be performed no less than 4 weeks after the criteria for response are first met. Longer intervals as determined by the study protocol may also be appropriate. In the case of SD, follow-up measurements must have met the SD criteria at least once after study entry at a minimum interval (in general, not less than 6-8 weeks) that is defined in the study protocol. For PD all results should be confirmed as described in section 8.2.

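### Appendix 6, read literally, scores unconfirmed growth on a patient's only follow-up scan as stable disease, a success in the Simon disease-control count, and accepts a single stable scan where section 10.1 asks for more

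*Combined protocol and SAP*

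**What the plan says.** **Which criteria govern.** Section 10.1 (Immune Related Response Criteria) sends the reader to Appendix 6 and uses those criteria to measure DCR and to "determine whether the study should proceed to stage 2". Section 12.1 sets the thresholds. Lymphoma needs more than 0 of 7, then more than 2 of 14. Solid tumor needs more than 1 of 16, then more than 3 of 30.

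**Appendix 6.**
- irPD is a rise in tumor burden of at least 25% "relative to nadir confirmed by a consecutive assessment" at least 4 weeks later.
- irSD is defined by exclusion: "Criteria for irCR, irPR, and irPD are not met; does not require confirmation".
- Best overall response is irSD given "At least one irSD and no irCR and no irPR".

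**Section 8.2 and Table 8.** "Subjects who are deemed clinically unstable or who have biopsy proven new metastatic lesions are not required to have repeat imaging for confirmation". For unstable patients Table 8 asks for a repeat scan at 4 or more "weeks to confirm PD if possible".

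**Section 10.1, other subsections.**
- Confirmation: "For PD all results should be confirmed as described in section 8.2". It also leaves the minimum interval for SD to the protocol, with 6-8 weeks as the general floor.
- Duration of Stable Disease: SD means two consecutive stable scans or four months. The text then recommends that the protocol set the interval.
- Reporting of Results: response categories 4 to 8 (progression, early death, unknown) are failures. The Simon analysis uses the evaluable patients of 12.4.

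**Section 12.4** removes only patients taken off treatment before the first CT/MRI scan. It has no scoring rule.

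**The concern.** Irrefutable growth and unrefuted growth are different things, and Appendix 6 has no class for the second. Growth that is never re-imaged cannot be irPD, so it falls into the residual class, which counts as disease control. Section 8.2 and Table 8 make this possible by not insisting on a repeat scan in patients who are deteriorating.

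The thresholds are low. One success in 7 opens lymphoma stage 2, and two in 16 open solid-tumor stage 2. The recommendation for a randomized trial rests on the same count. With numbers this small, the outcome should not depend on which passage the person scoring the scans follows after seeing the patient.

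The minimum for SD raises a second, separate conflict. It applies to any patient with one stable scan, not only to those with early growth.

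**Working it through.** **1. Classify one patient under each text.** Take a first scan at day 60 with tumor burden 40% above nadir, a clinically unstable patient, and no further scan.

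| Text | Result |
|---|---|
| Appendix 6, irCR and irPR | not met |
| Appendix 6, irPD | not met: no confirming assessment |
| Appendix 6, irSD and best response | met by exclusion: DCR success |
| 10.1 Confirmation, via 8.2 | repeat scan not required; points to PD |
| 10.1 Duration of Stable Disease | neither two stable scans nor four months |
| 10.1 Reporting of Results | failure, if classed as PD or unknown |
| 12.4 | stays in the count: first scan was done |

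**2. Who is affected.** All three conditions must hold: growth of at least 25% at the first post-baseline scan, no earlier irSD, irPR or irCR, and no later scan. Progression after an earlier irSD leaves best response at irSD in Appendix 6, so it adds nothing here.

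**3. Minimum for SD.** Day 60 is 60/7 = 8.6 weeks. One stable scan at day 60 satisfies Appendix 6 and the general 6-8 weeks in Confirmation. It does not satisfy two consecutive scans or four months. On the 60-day imaging calendar both of those fall at about day 120.

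**4. Reproduce the designs.** P(go) = sum over x > r1 of Bin(x; n1, p) × P[Bin(n − n1, p) ≥ r + 1 − x].
- Solid tumor (1/16, 3/30): 0.0478 at p = 0.05 and 0.807 at p = 0.20.
- Lymphoma (0/7, 2/14): 0.0274 at p = 0.05 and 0.810 at p = 0.30.

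Both agree with the stated one-sided 0.05 level and 80% power.

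**5. Conditional illustration.** Fix one stage-1 patient as a progressor, score that patient as failure or as SD, and leave all others at p = 0.05.

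Stage-1 pass:
- Lymphoma: 1 − 0.95^6 = 0.265 if failure. If SD it is 1.00, automatically, because r1 = 0.
- Solid tumor: P(at least 2 of 15) = 0.171 if failure, and 1 − 0.95^15 = 0.537 if SD.

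P(go), summed over successes among the other stage-1 patients:
- Lymphoma, SD: 0.7351 × 0.0444 + 0.2321 × 0.3017 + 0.0328 = 0.135.
- Lymphoma, failure: 0.2321 × 0.0444 + 0.0305 × 0.3017 + 0.0022 = 0.022.
- Solid tumor, SD: 0.3658 × 0.1530 + 0.1348 × 0.5123 + 0.0362 = 0.161.
- Solid tumor, failure: 0.1348 × 0.1530 + 0.0307 × 0.5123 + 0.0055 = 0.042.

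| True DCR | Cohort | No patient fixed | Scored failure | Scored SD |
|---|---|---|---|---|
| 5% | lymphoma | 0.027 | 0.022 | 0.135 |
| 5% | solid | 0.048 | 0.042 | 0.161 |
| 30% | lymphoma | 0.810 | 0.756 | 0.936 |
| 20% | solid | 0.807 | 0.776 | 0.929 |

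At a true DCR of 40%, lymphoma moves only from 0.915 to 0.987. That rate is the 20% response plus 20% stability that section 2.2 cites for earlier radiotherapy with CpG.

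**6. Assumed frequency.** The documents do not give the share f of true failures that fall in this group. With f assumed and every such patient scored SD, the success rate at a true 5% becomes 0.05 + 0.95f, and P(go) is:

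| f (assumed) | Solid | Lymphoma |
|---|---|---|
| 2% | 0.120 | 0.062 |
| 5% | 0.277 | 0.138 |
| 10% | 0.566 | 0.309 |
| 30% | 0.985 | 0.872 |

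The range shows sensitivity only. Nothing in the documents favors one row. Steps 5 and 6 concern unconfirmed growth and do not measure the SD-minimum conflict.

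**The case against.** The best reply is that section 10.1 already settles the example. Confirmation sits directly after the paragraph that selects Appendix 6, and it sends PD confirmation to 8.2, which waives the scan for unstable patients. Duration of Stable Disease would refuse the SD label, and Reporting of Results has an unknown category that fails. Appendix 6 itself derives best response once all assessments are complete, so a patient lost before the confirming scan arguably has none.

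Much of this stands. A reader might infer that the plan gives no guidance on such patients. It does, and the cross-reference to 8.2 is express. What remains is that 8.2 is written for treatment decisions and does not say that the patient is irPD for best response. The failure categories do not override an irSD label once it is given. Appendix 6, the named criteria, repeats none of these rules.

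Two further replies also stand in part. Patients removed before the first scan are replaced, so the earliest deteriorators never enter the count. New lesions only add to tumor burden in Appendix 6, so biopsy-proven spread without 25% growth is irSD by design.

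On the SD minimum, one can say that the two-scan or four-month rule supplies the interval that Confirmation leaves open. That is a fair reading. However, the next sentence still recommends that the protocol specify an interval, and Appendix 6 says that irSD needs no confirmation.

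**Conclusion.** Appendix 6 is wrong as written for the Simon DCR count. It conflicts with section 10.1 on two matters: growth with no repeat scan, and the minimum for SD. The first rests on a literal reading of the irSD definition and affects only the narrow group in step 2.

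A reader might infer from the figures that the designs miss their error rates, or that the trial's false-positive rate is 0.135 or 0.161. The documents do not support either. The designs reproduce, and those figures assume that one misscored patient is already present in stage 1. They show how far one patient can move the decision and do not estimate bias.

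Severity is minor to moderate. Sections 1.1.2 and 3 make safety the phase 2 primary (Table 10 also lists DCR as primary), and 12.4 calls efficacy results preliminary.

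**What to change.** Change endpoint scoring only and leave the treatment text of 8.2 as it is. Before the first stage-1 count, state in Appendix 6 and 12.4 that, for the Simon DCR:

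1. A patient whose only post-baseline evidence is an increase of at least 25% over nadir, with no later scan refuting it, is a DCR failure. This agrees with Confirmation, 8.2 and the failure categories.
2. The existing minimum in Duration of Stable Disease (two consecutive stable scans or four months) applies to irSD, so that Appendix 6 and both subsections of 10.1 agree.

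The second sentence does not make the first redundant. If progression is never confirmed, a reader could let the four-month clock run on.

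Optionally, note that the Table 8 footnote ("SD, PR, CR is based on new baseline from first evidence of PD") is not used for endpoint scoring. It sits in a treatment-management table, but Confirmation points to 8.2.

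The cost is a few sentences and no added scans. There are three downsides: a slightly lower reported DCR, a pseudo-progressor with no second scan counted as a failure, and SD known at about day 120 instead of day 60, which delays the stage-1 count for patients whose success is SD.
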